4.1 Confirmation of Patient Eligibility

Confirm patient eligibility by collecting the information listed below:

1. Registering MD’s name
2. Patient’s race, sex, and DOB
3. Three letters (or two letters and a dash) for the patient’s initials
4. Copy of signed consent form
5. Completed eligibility checklist, signed and dated by a member of the study team
6. Copy of appropriate source documentation confirming patient eligibility

4.2 Patient Registration in the Siteman Cancer Center OnCore Database

All patients must be registered through the Siteman Cancer Center OnCore database.

4.3 Assignment of UPN

Each patient will be identified with a unique patient number (UPN) for this study. All data will be recorded with this identification number on the appropriate CRFs.

5.0 TREATMENT PLAN

5.1 Agent Administration

Ramucirumab will be given intravenously over the course of an hour on an outpatient basis on Day 1 of each 21-day cycle at a dose of 10 mg/kg.

Atezolizumab will be given intravenously on an outpatient basis on Day 1 of each 21-day cycle at a dose of 1200 mg. The initial dose will be administered over 60 minutes (+/- 15 minutes). If the first infusion is tolerated without infusion-associated events, the second infusion may be delivered over 30 minutes (+/- 10 minutes).

Ramucirumab and atezolizumab may be given in any order on treatment days.

5.2 Toxicity and Response Evaluations

All patients who receive any study treatment are evaluable for toxicity. Patients are evaluated from first receiving study treatment until a 30-day follow up after the conclusion of treatment or death.

All patients are evaluable for disease response unless they discontinue treatment prior to completion of Cycle 2 and have not had any disease assessment.

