11.0 DATA SUBMISSION SCHEDULE

Case report forms with appropriate source documentation will be completed according to the schedule listed in this section.

Case Report Form	Submission Schedule
Original Consent Form	Prior to registration
On-Study Form	Prior to starting treatment
Treatment Form	Every cycle
Toxicity Form Concomitant Medications Form	Continuous. See Section 7.0 for reporting requirements
Research Tissue Form	Baseline, after Cycle 2/before Cycle 3
Research Blood Form	Baseline, C2D1
Treatment Summary Form	Completion of treatment
Follow Up Form	Every 3 months for 2 years
Death Form	Time of death
RECIST Form	Baseline, end of every even numbered cycle, and end of treatment
MedWatch Form	See Section 7.0 for reporting requirements

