14.2 Study Design

This single institution study will be designed using Simon's two-stage MiniMax design. We plan to enroll twenty-one (21) advanced-stage NSCLC patients.

Assuming a null hypothesis of ORR less than 5% in this setting, we hypothesize that ORR of 20% or higher warrants further investigation. A total number of 21 patients allows an 80% power at 1-sided alpha of 0.1 to detect the expected difference. If 4 or more responders are observed at the end of the trial, we would conclude that there is preliminary evidence for efficacy warranting further investigation.

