14.3 Data Analysis

Demographic and clinical characteristics of the sample, as well as toxicity by grade and loss to follow up will be summarized using descriptive statistics. Overall response rate (ORR) and clinical benefit rate (CBR) will be evaluated using the RECIST 1.1 criteria according to investigator's assessment, and their 1-side 90% confidence intervals will also be calculated. Kaplan-Meier product limit estimator will be used to describe the distribution of overall survival (OS) and progression free survival (PFS). The association between response and the immunophenotype of peripheral blood immune cells will be summarized using descriptive statistics. Although data analysis will be primarily descriptive, permutation test will be used to rank the strength of association. Specifically, we first compute the observed test statistics for the differences between responders and non-responders. Then the null distribution of the test statistics will be generated by simulating 10,000 datasets where the status of response was randomly shuffled. The permutation p-values equal the proportion of simulations from the null distribution that exceed the observed test statistics. Similar analysis will be performed for the association between response and the changes in tumor immune cell infiltrate after treatment.

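### The response-evaluable rule drops patients who stop before the first scan, so it can only leave ORR and CBR unchanged or raise them

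*Combined protocol and SAP*

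**What the plan says.** Section 5.2 defines two sets. For safety: "All patients who receive any study treatment are evaluable for toxicity". For response: "All patients are evaluable for disease response unless they discontinue treatment prior to completion of Cycle 2 and have not had any disease assessment".

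Section 14.3 describes the analysis: "Overall response rate (ORR) and clinical benefit rate (CBR) will be evaluated using the RECIST 1.1 criteria", by investigator assessment and with one-sided 90% confidence intervals. It names no analysis population, does not say how a patient without an assessment is counted, and plans no sensitivity analysis.

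Sections 10.0 and 12.1 place the response scans every two 21-day cycles, so the first falls at week 6. Section 11.0 makes the RECIST form due at "Baseline, end of every even numbered cycle, and end of treatment", but the Section 10.0 calendar marks no CT at the end-of-treatment visit.

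Section 14.2 sizes the trial on enrolled patients ("A total number of 21 patients allows an 80% power at 1-sided alpha of 0.1 to detect the expected difference") and decides on a count ("If 4 or more responders are observed at the end of the trial"). Section 1.6.1 keeps the total at 21 as a single enrolment. No section provides for replacing non-evaluable patients.

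**The concern.** A patient meets both exclusion conditions by stopping during the first six weeks without an extra assessment. Among the reasons for ending treatment, Section 5.5 lists death, adverse events and a change in the patient's condition. In this population these are mostly failures of treatment, so the exclusion depends on outcome. Section 12.4.3 does not rescue such cases: decline without objective progression is reported as symptomatic deterioration and given no response category.

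The primary objective is to determine the ORR, and the design reads it against two rates: "Assuming a null hypothesis of ORR less than 5% in this setting", and "we hypothesize that ORR of 20% or higher warrants further investigation". If early failures leave the denominator, the estimate and its lower limit describe patients who survived and tolerated treatment long enough to be scanned, not the 21 patients the trial was sized on. CBR suffers in the same way and has no count rule to fall back on.

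**Working it through.** **Inputs from the documents.** N = 21, null ORR 5%, target ORR 20%, one-sided alpha 0.1, power 80%, success at 4 or more responders (Section 14.2); one-sided 90% intervals (Section 14.3); first scan at week 6 (Sections 10.0 and 12.1).

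**Assumptions.** The number excluded, k, is not given; k = 1 to 4 is used. The 4 responders (the stated success count) and the 12 patients with clinical benefit are illustrations.

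**Step 1: the plan's own figure.** An exact Simon search for 5% against 20%, alpha at most 0.10 and power at least 0.80, gives a minimax design with 12 patients in stage 1 (stop if 0 respond), 21 in total and success at 3 or more. Its alpha is 0.080 and its power 0.803. So N = 21 and 80% power reproduce, with all 21 patients counted. (The stated cut-off of 4 or more gives alpha 0.019 and power 0.630 in a single stage of 21. That mismatch is a separate point.)

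**Step 2: direction.** An unassessed patient adds 0 to the numerator of either rate. With x events, the all-treated rate is x/21 and the evaluable rate is x/(21 − k). Their ratio is 21/(21 − k), never below 1: 1.05 for k = 1 (21/20) and 1.24 for k = 4 (21/17).

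**Step 3: size.** The lower limit is Clopper-Pearson: the 0.10 quantile of a Beta(x, n − x + 1) distribution, with n = 21 − k and x = 4.

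| k | n | ORR = 4/n | Lower 90% limit | CBR = 12/n |
|---|---|---|---|---|
| 0 | 21 | 19.0% | 8.6% | 57.1% |
| 1 | 20 | 20.0% | 9.0% | 60.0% |
| 2 | 19 | 21.1% | 9.5% | 63.2% |
| 3 | 18 | 22.2% | 10.1% | 66.7% |
| 4 | 17 | 23.5% | 10.7% | 70.6% |

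Both rates are multiplied by the same factor. The shift in percentage points is larger for CBR because CBR is the larger rate: at k = 4, about 13 points against about 4.5 for ORR.

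**Step 4: fewer responders.** At k = 4, one responder moves from 1/21 = 4.8% to 1/17 = 5.9%, and two from 2/21 = 9.5% to 2/17 = 11.8%. With none, ORR stays at 0%.

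**Step 5: the count rule.** With 21 enrolled and no replacement, the number of responders is the same under either denominator, so the error rates of the rule do not change. If non-evaluable patients were replaced until 21 were evaluable (an assumption; the documents do not say so), and a fraction d of treated patients were non-evaluable, a true all-treated ORR of 5% would become 0.05/(1 − d) among the evaluable: 5.6% for d = 10% and 6.3% for d = 20%. The chance of 4 or more responders would rise from 0.019 to 0.027 and 0.039.

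**The case against.** The strongest reply is that the trial's decision is untouched. Section 14.2 decides on a count, no replacement is described, and 20% is the design alternative rather than a bar for the observed rate: 4 of 21, at 19.0%, already succeeds. All of that stands. It limits the consequence to the estimates and intervals, but those are what the primary objective and Section 14.3 ask for.

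Second, no sentence says that ORR is divided by the evaluable set, and Section 1.6.1 reports results over all 12 initial patients. The denominator is indeed inferred. But Section 5.2 is the only rule on who counts for response, and its definition has no other stated use. If all 21 are meant, the plan does not say so, and the denominator of the primary endpoint could be settled after the results are known.

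Third, the exclusion is narrow. Both conditions must hold, any assessment keeps a patient in, Section 11.0 asks for a RECIST form at end of treatment, and Section 12.4.3 urges documenting progression after treatment stops. This may keep k small. It does not make it zero, because the calendar has no end-of-treatment CT and a patient who dies early may have had no assessment.

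Fourth, some early stops are not failures: Section 5.5 also lists withdrawal of consent and loss to follow-up. Counting these as non-responders is a conservative convention, but they have no recorded response either.

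Fifth, Section 1.6.1 reports no responses in the first 12 patients. Unless one of them responds later, 4 responders must come from the last 9, which has a probability of about 8.6% at a true ORR of 20%. The 4-responder illustration is therefore at the favourable end. Early deaths also remain visible in OS, PFS and toxicity. Neither point changes the direction of the bias.

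**Conclusion.** The concern holds. Followed as written, Section 5.2 can only leave ORR and CBR unchanged or raise them, by the factor 21/(21 − k), and no other section corrects it. The direction is certain. The size rests on k, which the documents do not give: it is nil if every treated patient has an assessment, and a relative inflation of 5% to 24% for 1 to 4 exclusions. The decision rule is unaffected without replacement. The point is therefore one of biased estimation and reporting of the primary endpoint and one secondary endpoint. The plan should be changed, though the go decision does not depend on it.

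**What to change.** In Sections 5.2 and 14.3, set the denominator for ORR and CBR to all patients who received any study treatment, the set Section 5.2 already uses for toxicity. State that a patient with no post-baseline disease assessment counts as a non-responder and as having no clinical benefit. Keep the present evaluable set as a sensitivity analysis only, and say there that the assessment meant is a post-baseline one. Report the number of patients in each set, with the reasons for exclusion.

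The cost is about two sentences. No new data, visits or patients are needed. Where k is above zero, ORR (if there is any responder) and CBR will be somewhat less favourable than under the present rule.

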5.3 General Concomitant Medication and Supportive Care Guidelines

5.3.1 Ramucirumab

Patients may not be receiving chronic antiplatelet therapy, including aspirin, nonsteroidal anti-inflammatory drugs (NSAIDs, including ibuprofen, naproxen, and others), dipyridamole or clopidogrel, or similar agents. Once-daily aspirin use (maximum dose 325 mg/day) is permitted.

Patients who experience infusion-associated symptoms may be treated symptomatically with diphenhydramine, and/or cimetidine or another H2 receptor antagonist, as per standard practice (for sites outside the United States, equivalent medications may be substituted per local practice).

In the event of additional reaction, systemic hydrocortisone or another corticosteroid may be administered at the discretion of the treating physician.

Montelukast will be administered daily for 7 days, starting 6 days prior to treatment with the final dose on Day 7, per the treating physician's discretion.

5.3.2 Atezolizumab

Concomitant therapy includes any prescription medications or over the counter preparations used by a patient between the 7 days preceding the screening evaluation and the treatment discontinuation visit.

Patients who experience infusion-associated symptoms may be treated symptomatically with acetaminophen, ibuprofen, diphenhydramine, and/or cimetidine or another H2 receptor antagonist, as per standard practice (for sites outside the United States, equivalent medications may be substituted per local practice). Serious infusion associated events manifested by dyspnea, hypotension, wheezing, bronchospasm, tachycardia, reduced oxygen saturation, or respiratory distress should be managed with supportive therapies as clinically indicated (*e.g.*, supplemental oxygen and β_2 -adrenergic agonists).

Systemic corticosteroids and TNF α inhibitors may attenuate potential beneficial immunologic effects of treatment with atezolizumab but may be administered at the discretion of the treating physician. If feasible, alternatives to corticosteroids should be considered. Premedication may be administered for Cycles ≥ 2 at the discretion of the treating physician. The use of inhaled corticosteroids and mineralocorticoids (*e.g.*, fludrocortisone) for patients with orthostatic hypotension or adrenocortical insufficiency is allowed. Megestrol administered as appetite stimulant is acceptable while the patient is enrolled in the study.

Patients who use oral contraceptives, hormone-replacement therapy, prophylactic or therapeutic anticoagulation therapy (such as low-molecular-weight heparin or warfarin at a stable dose level), or other allowed maintenance therapy should continue their use. Females of reproductive potential should use highly effective means of contraception.

It is strongly recommended that:

- Traditional herbal medicines not be administered because the ingredients of many herbal medicines are not fully studied and their use may result in unanticipated drug-drug interactions that may cause, or confound assessment of, toxicity.
- The use of a RANKL inhibitor (denosumab) be discontinued during the study; this agent could potentially alter the activity and the safety of atezolizumab.

Patients are not allowed to receive immunostimulatory agents, including, but not limited to, IFN- α , IFN- γ , or IL-2, during the entire study. These agents, in combination with atezolizumab, could potentially increase the risk for autoimmune conditions.

Patients should also not be receiving immunosuppressive medications, including, but not limited to, cyclophosphamide, azathioprine, methotrexate, and thalidomide. These agents could potentially alter the activity and the safety of atezolizumab. Systemic corticosteroids and anti-TNF α agents may attenuate potential beneficial immunologic effects of treatment with atezolizumab but may be administered at the discretion of the treating physician. If feasible, alternatives to these agents should be considered.

In addition, all patients (including those who discontinue the study early) should not receive other immunostimulatory agents for 10 weeks after the last dose of atezolizumab.

5.4 Women of Childbearing Potential

Women of childbearing potential (defined as women with regular menses, women with amenorrhea, women with irregular cycles, women using a contraceptive method that precludes withdrawal bleeding, and women who have had a tubal ligation) are required to have a negative serum pregnancy test within 7 days prior to the first day of study treatment.

Female and male patients (along with their female partners) are required to use two forms of acceptable contraception, including one barrier method, during participation in the study and for 6 months following the last day of study treatment.

If a patient is suspected to be pregnant, both study drugs should be immediately discontinued. In addition a positive urine test must be confirmed by a serum pregnancy test. If it is confirmed that the patient is not pregnant, the patient may resume dosing.

If a female patient or female partner of a male patient becomes pregnant during therapy or within 6 months after the last day of study treatment, the investigator must be notified in order to facilitate outcome follow-up.

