10. Women of childbearing potential and men must agree to use adequate contraception (hormonal or barrier method of birth control, abstinence) prior to study entry and for the duration of study participation. Should a woman become pregnant or suspect she is pregnant while participating in this study, she must inform her treating physician immediately.

11. Ability to understand and willingness to sign an IRB approved written informed consent document (or that of legally authorized representative, if applicable).

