5.5 Duration of Therapy

If at any time the constraints of this protocol are considered to be detrimental to the patient's health and/or the patient no longer wishes to continue protocol therapy, the protocol therapy should be discontinued and the reason(s) for discontinuation documented in the case report forms.

In the absence of treatment delays due to adverse events, treatment may continue indefinitely or until one of the following criteria applies:

- Documented and confirmed disease progression
- Death
- Adverse event(s) that, in the judgment of the investigator, may cause severe or permanent harm or which rule out continuation of study drug
- General or specific changes in the patient's condition render the patient unable to receive further treatment in the judgment of the investigator
- Suspected pregnancy
- Serious non-compliance with the study protocol
- Lost to follow-up
- Patient withdraws consent
- Investigator removes the patient from study
- The Siteman Cancer Center decides to close the study

Patients who prematurely discontinue treatment for any reason will be followed as indicated in the study calendar.

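### The contraception agreement in Section 3.1 item 10 can be met without meeting Section 5.4, and Sections 5.4 and 5.5 give different outcomes for suspected pregnancy

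*Combined protocol and SAP*

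**What the plan says.** Contraception is addressed in three places.

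- **Section 3.1, item 10.** The entry agreement, asked of men and of women who could become pregnant, covers "adequate contraception (hormonal or barrier method of birth control, abstinence) prior to study entry and for the duration of study participation".
- **Section 5.3.2.** "Females of reproductive potential should use highly effective means of contraception". The term is not defined, no number of methods or duration is given, and men are not mentioned.
- **Section 5.4.** Patients of both sexes, together with the female partners of male patients, "are required to use two forms of acceptable contraception, including one barrier method". The rule runs through participation and then for a further 6 months from the last treatment day.

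Suspected pregnancy is addressed in two.

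- **Section 5.4.** Both drugs are stopped at once and a positive urine test is checked by a serum test. Then: "If it is confirmed that the patient is not pregnant, the patient may resume dosing".
- **Section 5.5.** Treatment may go on until one of a list of criteria applies. One entry reads, in full, "Suspected pregnancy". It has no confirmation step and no reference to 5.4.

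**The concern.** An inclusion criterion and a treatment rule on the same precaution should ask for the same thing. Here the criterion that decides entry asks for less than the section that governs patients on treatment, and no cross-reference or order of precedence says which one controls. A patient could do exactly what was agreed at entry and be out of compliance with 5.4 from the first dose. That has consequences within the protocol: Appendix B classes departures from the approved research as deviations, major ones if they could affect safety, and Section 5.5 lists serious non-compliance as a reason to end treatment.

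For suspected pregnancy, two members of staff could each follow the protocol and act in opposite ways. One would hold the drugs, confirm, and resume after a negative result. The other would take the patient off treatment on suspicion alone.

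**Working it through.** No arithmetic applies. The plan gives no figure on this point, and none of its sample size, power or alpha depends on it. The check is to set the rules side by side.

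| | 3.1 item 10 | 5.3.2 | 5.4 |
|---|---|---|---|
| Who | Women of childbearing potential, and men | Females of reproductive potential | Female and male patients, with female partners |
| Force | Must agree, as a condition of entry | Should | Required |
| Methods | One (hormonal or barrier), or abstinence | Number not given | Two, one of them a barrier |
| Abstinence | Accepted | Not mentioned | Not mentioned |
| After last treatment day | No period stated | No period stated | 6 months |

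**Step 1: number of methods.** Take a patient who relies on one hormonal method, or on abstinence alone. Item 10 is met. The two-method rule in 5.4 is not. This holds however the duration is read.

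**Step 2: duration.** Item 10 applies "prior to study entry and for the duration of study participation". Study participation is not defined, so there are two readings.

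- If it ends with treatment, item 10 stops there and 5.4 runs 6 months longer.
- If it includes the follow-up in Section 5.6 (every 3 months for 2 years, or until death), item 10 could run past the 6-month mark.

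Section 5.4 names participation and the 6 months separately, which favours the narrower reading, because on the wider one the 6-month clause would be largely redundant. The text does not settle it. What can be said is that the post-treatment period is stated in 5.4 and not in 3.1.

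**Step 3: Section 5.3.2.** An undefined standard with no number and no duration differs in wording from the other two. It does not strictly contradict two methods including a barrier.

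**Step 4: suspected pregnancy.** In 5.4 the sequence is suspicion, stop, test, and possible resumption. In 5.5 suspicion is itself a listed end-of-treatment criterion, beside death and confirmed progression. For a patient whose pregnancy is ruled out, 5.4 allows treatment to continue and the 5.5 list, read as written, does not.

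**The case against.** The strongest reply on contraception is that both rules can be followed at once. A patient using one hormonal and one barrier method meets item 10 and 5.4 together, and nothing in 3.1 releases an enrolled patient from 5.4. On this view item 10 is a minimum at entry and 5.4 the stricter rule on treatment. That is fair as far as it goes: neither rule makes the other impossible. But the entry agreement can be met without meeting 5.4, and item 10 itself reaches through participation, so it is not confined to the moment of entry.

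On suspected pregnancy, 5.4 can be read as the specific procedure and 5.5 as a summary list. Section 5.4 itself speaks of discontinuing the drugs and then allows resumption. Staff may well read it that way, but the protocol does not say so.

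Other safeguards agree with one another: a negative serum test within 7 days, a duty to report a suspected pregnancy, the immediate stop of both drugs, and notification of pregnancies up to 6 months after treatment. These limit the consequences without removing the contradictions.

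Three stronger readings are tempting, and the documents do not support them.

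- **That patients consent to weaker protection.** The consent pages are not among the documents available for review, so what patients sign cannot be checked. Section 4.1 requires a completed eligibility checklist but does not show its content. The supportable statement concerns the inclusion criterion only.
- **That 3.1 sets no post-treatment protection at all.** It states no period; that is not the same as stating none, as step 2 shows.
- **That a patient wrongly taken off treatment shifts the response rate.** This would require someone who would have responded and had not yet done so. Section 5.2 keeps patients evaluable unless they stop before completing Cycle 2 with no disease assessment, and Section 11 schedules a RECIST form at end of treatment. No frequency is given either.

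**Conclusion.** Wrong as written, in two respects.

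1. Item 10 of Section 3.1 can be met with one method or abstinence, for an undefined period, while 5.4 requires two methods including a barrier, through participation and 6 months beyond treatment. The difference in methods holds on any reading. The difference in duration is one of stated wording, and its practical extent depends on what study participation means.
2. Section 5.4 makes the stop for suspected pregnancy reversible; 5.5 lists it without qualification as ending treatment.

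Section 5.3.2 adds a third, undefined wording that should be aligned but is not a direct conflict.

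The conclusion rests only on the text of these sections and on the absence of a precedence rule between them. It is a matter of patient safety and internal consistency. It does not touch the sample size, the response-rate endpoint or the 4-responder decision rule. It should be corrected, but it is not a threat to the trial's primary conclusion.

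**What to change.** In one amendment:

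- Reconcile 3.1 item 10 and 5.4 into a single contraception requirement that states the methods, whether abstinence is accepted, and the duration, including any post-treatment period. Either define study participation or give the period without relying on that term.
- Align the wording of 5.3.2 with that requirement, or replace it with a cross-reference.
- Reconcile the suspected-pregnancy entry in 5.5 with the resume provision in 5.4, with a cross-reference between them.
- Check that the eligibility checklist and the consent form carry the same statement.

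The sponsor decides which clinical rule applies; the request is only that the sections agree. The cost is wording changes, with no change to sample size, endpoints or analysis.
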